8.2 Information of Investigators

An Investigator's Brochure will be handed out to the Investigator before the start of the study. This Brochure contains all information in the Sponsor's possession necessary for the Investigator to be fully and accurately informed about the safety of the IMP under evaluation and the respective benefit-risk ratio.

The Investigator's Brochure will be updated by the Sponsor at regular intervals and in case new information concerning the IMP becomes available.

The Investigators will be informed about the methods for rating relevant study outcomes and for completing CRFs in order to reduce discrepancies between participating Investigators and study sites.

The Investigator will be kept informed of important data that relate to the safe use of the IMP as the study proceeds.

8.3 Responsibilities

The Sponsor provides the study medication (NewGam). In this role, the Sponsor can be contacted in case of medical issues and is responsible for the assessment of the reported SAEs as well as for the further distribution to the relevant regulatory authorities.

The Co-ordinating Investigator of this study is [REDACTED]

The Principal Investigator is accountable for the conduct of the clinical study. Responsibilities may be delegated to appropriately qualified persons.

A „Delegation of Authority Log“ will be filled in and signed by the Principal Investigator. In accordance with this authority log, study site staff (e.g., sub-Investigators, nurses) is authorized to perform tasks relating to the study.

Monitoring will either be done by the Sponsor or by a subcontractor (to be appointed later).

Study data management and statistics and EDC system will be delegated under an agreement of transfer of responsibilities to an external CRO and/or third party vendor. All Octapharma procedures and policies have to be met by this CRO/third party vendor, discrepancies or exceptions are to be approved by Octapharma's Manager of Biometrics.

An Independent Data Monitoring Committee (IDMC) will be installed to observe the safety throughout the trial. The detailed obligations and procedures will be laid down in a written procedure provided by the Sponsor.

All laboratory tests (hematology, clinical chemistry, virology and urinalysis) will be done centrally.

NCS will be centrally reviewed by [REDACTED].

All parties involved in the study are responsible to comply with local and international obligations, regulatory requirements and duties in accordance with local laws, ICH-GCP E6 and GLP guidelines, SOPs and other applicable regulations.

8.4 Investigator's Site File

At each study site, the Investigator is responsible for maintaining all records to enable the conduct of the study to be fully documented. Essential documents as required by ICH-GCP E6 guidelines and regulations (e.g., copies of the protocol, study approval letters, all original informed consent forms, a blank print-out of the e-CRF, drug dispensing and accountability logs, correspondence pertaining to the study, etc.) should be filed accurately and kept by the Investigator for the maximum period of time required by local regulations.

The Investigator is responsible for maintaining a confidential patient identification code list, which provides the unique link between named source records and eCRF data for the Sponsor. The Investigator must arrange for the retention of this confidential list for the maximum period of time required by local regulations.

No study document should be destroyed without prior written agreement between the Investigator and the Sponsor. Should the Investigator elect to assign the study documents to another party, or move them to another location, the Sponsor must be notified in writing.

8.5 Provision of Additional Information

On request, the Investigator will supply the Sponsor with additional data relating to the study, or copies of relevant source records, ensuring that the patient's confidentiality is maintained. This is particularly important when errors in data transcription are encountered. In case of particular issues or governmental queries, it is also necessary to have access to the complete study records, provided that the patient's confidentiality is protected in accordance with applicable regulations.

8.6 Independent Data Monitoring Committee

An Independent Data Monitoring Committee (IDMC) will be established by the Sponsor. The IDMC will be composed of recognized experts in the field of peripheral neuropathy who are not actively recruiting patients.

The IDMC will review relevant data periodically during the study and will give advice on the continuation, modification or termination of the study. A written study specific procedure will define in detail the composition, responsibilities and procedures of the IDMC.

8.7 Steering Committee

A Steering Committee will be established to medically/scientifically advise and guide the Sponsor during the study progress. The Steering Committee will be responsible for overall study overview, may give recommendations for protocol amendments after discussion with the Sponsor and may be involved in publication writing together with the DMC members and Co-

ordinating Investigator. It will consist of at least three national coordinating investigators and/or internationally well-known CIDP experts with experience in conducting clinical trials.

9 STATISTICAL METHODS AND SAMPLE SIZE

The statistical analysis will be delegated under an agreement of transfer of responsibilities to an external CRO. All Octapharma procedures and policies have to be met by this CRO. Discrepancies or exceptions are to be approved by the Sponsor's Manager of Biometrics.

9.1 Determination of Sample Size

The sample size calculation is based on the proportion of responders in the 1.0 g/kg dose group. This dose regimen is the currently most commonly used for maintenance IGIV doses in CIDP. Recent experiences with this dosing regimen are available from the ICE study [24] and the PRIMA trial.[25] In both of these studies, the lower confidence limit of the 95% Wilson-Score confidence interval for the proportion of responders (R) was 42% if rounded to the nearest integer, and thus we have also chosen 42% as the threshold for the following pair of hypotheses for evaluation of the primary endpoint:

[figure not shown]
$$H_0: R < 0.42$$

$$H_1: R \geq 0.42$$

This will be tested by comparing the lower limit of the 95% Wilson-Score confidence interval for the observed proportion of responders with the pre-defined threshold of 0.42.

We estimate the true percentage of responders in CIDP patients treated with NewGam as 60%. This corresponds to the 60.7% of responders observed in the PRIMA study, but is higher than the outcome in the ICE (54.2%), that in the opinion of many experts underestimates the true percentage of responders.

We applied these parameters to a computer simulation realized in SAS to determine the statistical power associated with various group sizes:

To achieve a power of at least 80%, a minimum of 62 evaluable patients in the 1.0 g/kg dose group will be needed; to account for possible dropouts we plan to enroll 70 patients into this group.

In order to allow for the comparison between dose groups, ProCID will enroll half of the eligible patients in the standard dose arm (1.0 g/kg NewGam) and the other half into the lower and higher dose arms (0.5 g/kg and 2.0 g/kg NewGam), resulting in a total of 124 evaluable patients, and an enrollment target of 140 patients overall (ratio: 1:2:1 for 0.5 g/kg, 1.0 g/kg, and 2.0 g/kg, respectively).

9.2 Statistical Analysis

A formal statistical analysis plan describing all details of the analyses to be performed will be prepared by the study statistician and approved by the Sponsor prior to unblinding and the start of the statistical analysis.

Data tabulations will comprise the results for the different dose groups and for the whole analysis set whenever appropriate. Evaluation of primary and secondary endpoints will be presented for each randomization stratum (prior treatment with Immunoglobulins or Corticosteroids) separately to facilitate the identification of noteworthy differences in the clinical responses between these two groups. No further subgroup analyses are pre-specified for this study, but the different CIDP variants eligible for enrollment, such as Multifocal Acquired Demyelinating Sensory And Motor Neuropathy (MADSAM) or pure motor CIDP, will be compared with respect to dose group, INCAT score and proportion of response as well. If indicated by the data, further comparisons between these CIDP variants will be added post-hoc.

9.2.1 Population for Analysis

The following populations will be considered for the statistical analysis:

The safety set (SAF) will include all randomized patients who received at least part of one infusion of IMP.

The full analysis set (FAS) is defined according to the intention-to-treat principle, and will include all patients of the SAF who satisfy all major entry criteria – in particular the diagnosis of CIDP – and for whom any data was collected post infusion of IMP. Every treated subject will be considered in the analysis according to his randomized treatment/dose assignment.

The per-protocol set (PPS) – being a subset of the FAS — will exclude patients with significant protocol deviations, which may have an impact on the evaluation of the primary study outcome parameter(s). This is the set of patients who participated in the study as intended and for whom the primary efficacy endpoint can be evaluated as planned.

All protocol deviations documented during the conduct of the study or identified at the data review process prior to DB lock will be reviewed and classified with respect to its effect on the planned analysis. Only protocol violations with the potential to significantly affect the study results or to invalidate the interpretation of the data obtained will lead to exclusion of patients from the PPS. This classification of protocol violations is the joint responsibility of the clinical study manager, the study statistician, and Octapharma's responsible medical expert, and will be performed and documented before the database is locked, the data is unblinded, and the statistical analyses are performed.

Protocol deviations to be considered will include (but are not limited to):

- Deviations of the study entry criteria
- Administration of any other blood or plasma-derived product or of any other immunoglobulin preparations
- Any prohibited concomitant medication
- Failure to attend two scheduled consecutive visits OR three or more scheduled visits during the study for reasons other than clinical reasons

The analysis of safety will be based on the safety set.

The evaluation of primary objective(s) will be performed for the FAS (intention-to-treat analysis) and for the PPS (per-protocol analysis). The ITT analysis is considered to be the most relevant, and will be presented first in the statistical report.

The evaluation of secondary objectives will be performed for the FAS, and in addition for the PPS in case the two populations differ by more than 5%

9.2.2 Efficacy Analysis Plan

Efficacy will be evaluated by a variety of commonly used parameters to assess the severity and progression of CIDP, with the adjusted INCAT disability score being the most important parameter. The primary efficacy endpoint will thus be the proportion of responders in the 1.0 g/kg NewGam arm, where a responder is defined as a patient with a decrease of at least 1.0 point on the adjusted INCAT disability score at Week 24 relative to Baseline.

Confirmatory statistical testing of the primary endpoint will be done by constructing the 95% Wilson-Score confidence interval for the proportion of responders, and comparing the lower confidence limit with the predefined threshold of 0.42. This corresponds to a one-sided test of the following pair of hypotheses at the $\alpha=0.025$ confidence level.

$$H_0: R < 0.42$$

$$H_1: R \geq 0.42$$

Where R is the proportion of responders i.e. the number of patients in the FAS who are responders according to the abovementioned definition, divided by the total number of patients in the FAS.

This evaluation will also be presented for the PPS to assess the robustness of the primary study endpoint with respect to protocol violations.

To assess and compare the effectiveness of the different dose groups, these will be presented side-by-side in descriptive statistics, including the 95% confidence intervals for the proportion of responders. In addition the response rates in the alternative dose groups will be compared descriptively to the 1.0 g/kg treatment group by presenting the confidence intervals for the differences; furthermore an exploratory logistic regression, that includes the pre-treatment as well as the dose group as predictor variables, will be conducted.

All efficacy endpoints detailed in Sections 3.1.2 and 3.1.3 will be summarized by means of descriptive statistics, presented graphically as appropriate, and listed in full detail. Tables and graphs will allow for direct comparison of the different dose groups whenever feasible. A similar logistic regression as for the primary endpoint will also be used for the secondary response variables (based on grip strength or I-RODS scores).

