3.1.2 Secondary Endpoints

Efficacy:

- Proportion of responders in the 0.5 g/kg and 2.0 g/kg NewGam arms at Week 24 relative to baseline at Week 0 compared to the 1.0 g/kg arm, based on the adjusted INCAT disability score
- Proportion of responders in the 0.5 g/kg and 2.0 g/kg NewGam arms at Week 24 relative to baseline at Week 0 compared to the 1.0 g/kg arm, based on the grip strength (Martin Vigorimeter) using the previously published minimum clinically important difference (MCID) cut-off of 8 kPa.[26]
- Proportion of responders in the 0.5 g/kg and 2.0 g/kg NewGam arms at Week 24 relative to baseline at Week 0 compared to the 1.0 g/kg arm, based on the I-RODS scores using the MCID concept related to the varying standard errors (MCID-SE) as recently demonstrated.[27]
- Time to first confirmed worsening on the adjusted INCAT disability scale by at least 1 point from the value at Baseline
- Mean change from Baseline (Week 0) to Termination Visit in
 - grip strength of both hands (assessed by Martin Vigorimeter) Inflammatory Rasch-built Overall Disability Sum Score (I-RODS using the concept of MCID-SE as recently reported; [Appendix 1](#)) and number of improvers
 - sum of the distal evoked amplitude of 4 right sided and 4 left sided motor nerves (peroneal, tibial, ulnar and median)
 - Pain Intensity Numeric Rating Scale (PI-NRS)
- Time to first confirmed worsening on the I-RODS scale
- Time to 1 point decrease (improvement of disability) in adjusted INCAT disability score
- Time to decrease in I-RODS scores

¹ The adjusted INCAT score is identical to the original INCAT disability score with the exception that upper extremity score changes from 0 (normal) to 1 (minor symptoms) or from 1 to 0 are excluded in determining the adjusted score, given that these changes are not considered clinically meaningful.

Safety:

Throughout the entire 24-week Dose-evaluation Phase:

- Occurrence of all adverse events (AEs)
- Short term tolerance parameters including vital signs
- Physical/neurological examination
- Laboratory parameters (hematology and clinical chemistry) and tests for viral safety
- Standard ECG (only at screening visit)

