octa pharma

Statistical Analysis Plan

Study ID NGAM-08

[figure not shown]
Study title Prospective, Double-Blind, Randomized, Multicenter Phase III Study Evaluating Efficacy and Safety of Three Different Dosages of Newgam in Patients With Chronic Inflammatory Demyelinating Poly(Radiculo)Neuropathy (ProCID study)

Study phase III

Document author
Document version
Final 03
Supersedes
2.0
Effective date
06-Jun-2019
Doc ID
2969

Protocol version this SAP is based upon Version 04 (dated 08-JUN-2018)

Approved by

Document History

Version	Date	Author	Description
Final v1	17-Dec-2015		New document
Final v2	16-Dec-2016		Incorporation of protocol changes based on FDA feedback to protocol version 1. Specifications with respect to the randomization strata.
Final v3	06-Jun-2019		Incorporation of protocol changes (v4)
			Details added on planned statistical analyses: Primary endpoint: Logistic regression
			Secondary endpoints: ANCOVA for changes from baseline in I-RODS total score; grip strength; MRC sums score; FSS total score; NCS measurements; QoL scores; ANCOVA models will be used for LSMEANS calculation (+95% CI) in various subgroups
			Logistic regression for responses based on I-RODS; based on grip strength; based on MRC sum score
			For INCAT disability total score and PI-NRS 95% confidence intervals for the median are added.
			Kaplan-Meier analysis for time-to response variables
			Deterioration after Wash-out/during dose evaluation added

Abbreviations

AE	Adverse Event
ВМІ	Body Mass Index
CI	Confidence Interval
CIDP	Chronic Inflammatory Demyelinating Poly(Radiculo)Neuropathy
CSR	Clinical Study Report
DB	Database
ECG	Electrocardiogram
(e)CRF	(Electronic) Case Report Form
EFNS	European Federation of Neurological Societies
FAS	Full Analysis Set
FDA	Food and Drug Administration

ITT	Intention-To-Treat			
I-RODS	Inflammatory Rasch-built Overall Disability Scale			
IWRS	Interactive Web Response System			
MADSAM	Acquired Demyelinating Sensory And Motor Neuropathy			
MCS Mental Composite Score MedDRA Medical Dictionary for Regulatory Activities MRC Medical Research Council				
		NAT		
		NCS		
PCS Physical Composite Score				
PNS	Peripheral Nerve Society			

Statistical Analysis Plan for NGAM-08

FSS	Fatigue Severity Scale	
GCP	Good Clinical Practice	
HBV	Hepatitis B Virus	
HCV	Hepatitis C Virus	
HIV	Human Immunodeficiency Virus	
ICH	International Conference on Harmonisation	
IgG	Immunoglobulin G	
IGIV	Intravenous Immunoglobulin	

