7.1. Subgroups

In addition to combined presentations over all strata, evaluation of the primary endpoint will be presented for each randomization stratum (prior treatment with Immunoglobulins or Corticosteroids) separately to facilitate the identification of noteworthy differences in the clinical responses between these two groups.

The different CIDP variants eligible for enrollment, such as Multifocal Acquired Demyelinating Sensory And Motor Neuropathy (MADSAM) or pure motor CIDP, will be compared with respect to dose group and proportion of response as well.

Additional analyses, such as logistic regression or ANCOVA, will be deployed for primary and secondary endpoints to further examine differences between subgroups in an exploratory manner. The ANCOVA models will also be used for least square means calculation including 95% confidence intervals in various subgroups (see section 10.2).

8. General Issues for Statistical Analysis

Descriptive summaries will be presented for each of the primary, secondary and exploratory variables. In general, summaries will be completed for all patients overall and by dose group, and the data will be presented by means of standard summary statistics according to the different types of data:

- Binary data (whether or not an event has occurred): counts and proportions
- Count data (the frequency of an event in a set time period): rate (count per unit time)
- Continuous data (measurements on a continuous scale, including quasi-continuous variables): arithmetic mean, standard deviation, median, minimum, maximum
- Scales data (Ordinal and Non-ordinal): absolute and relative frequencies
- Time-to-event data (how long it takes to observe the outcome of interest: time to event or last evaluation (censored data in case patients are lost to follow-up) and event rate). These parameters might not be tabulated separately, but can be included as an inset into a Kaplan-Meier plot of the product-limit survival function estimates.

Additional descriptive and exploratory statistics, such as geometric means, quartiles or confidence intervals, are included as appropriate. If not mentioned otherwise, confidence intervals are to be understood as two-sided, 95% confidence intervals.

In general the denominator for calculating percentages will be the total number of patients in the analysis population unless otherwise specified.

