9.4. Measurement of Treatment Compliance

The following parameters will be listed and summarized per patient and/or per infusion:

- Body weight
- Actual dose (total and per kg body weight, based on the latest available weight measurement)
- Total dose of NewGam administered
- Total number of infusions administered
- Total volume of solution administered
- Infusion times
- Overall amount of product administered (only included in data listings)
- Infusion rates

Deviations from the planned treatment schedule will be summarized by counting the number of infusions that deviate from the scheduled intervals by more than 4 days, and by listing all cases with more than 4 days deviation individually.

10. Efficacy Analysis

The primary objective of this study is to confirm the efficacy of NewGam in patients with CIDP that were observed in published clinical studies by evaluating the proportion of responders in the 1.0 g/kg dose group.

This study will furthermore compare all efficacy endpoints between the different dosing groups.

Formal planned analyses are described below. It may be necessary for additional exploratory analyses to be performed after the results from the planned analysis are completed; in this case full details of additional analyses will be given in the CSR.

The evaluation of the primary endpoint will be performed for the FAS and for the PPS. The evaluation of secondary endpoints will be performed for the FAS, and in addition for the PPS in case the two populations differ by more than 5%. The FAS analysis is considered to be the primary assessment of efficacy, and will be presented first in the report.

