10.1. Primary Efficacy Variable Analysis

The primary efficacy variable is the proportion of responders in the 1.0 g/kg NewGam arm at Week 24 (Termination Visit) relative to baseline (Week 0). A responder being defined as a patient with a decrease of at least 1 point on the adjusted INCAT disability score.

Confirmatory statistical testing of the primary endpoint will be done by constructing the 95% Wilson-Score confidence interval for the proportion of responders, and comparing the lower confidence limit with the predefined threshold of 0.42. This corresponds to a one-sided test of the following pair of hypotheses at the α =0.025 confidence level.

 H_0 : R < 0.42

 $H_1: R \ge 0.42$

Where *R* is the proportion of responders i.e. the number of patients in the FAS who are responders according to the abovementioned definition, divided by the total number of patients in the FAS.

This evaluation will also be presented for the PPS to assess the robustness of the primary study endpoint with respect to protocol deviations.

To assess and compare the primary efficacy endpoint also between the different dose groups, and also between the randomization strata (by dose group and over all dose groups) the proportion of responders will be presented side-by-side, including the 95% confidence intervals.

The time to first response and time to first worsening will be examined and presented by means of a Kaplan-Meier analysis.

Additional analyses, such as logistic regression- will be deployed to further examine any noteworthy differencesin an exploratory manner. The logistic regression model for analysis of response will include dose group, randomization stratum and CIDP variant (typical vs. atypical) as factors and baseline score as covariate. Odds ratios will be calculated to compare response rates between the factor levels, these will be presented together with 95% confidence intervals.

Moreover the proportion of responders after having provided rescue medication will be calculated with respect to all patients who received rescue medication and will be presented by dose group and overall, together with 95% confidence intervals.

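### The four secondary time-to-event endpoints get Kaplan-Meier analysis but no between-dose estimate with an interval; adding an exploratory one is a cheap improvement

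*Protocol*

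**What the plan says.** Protocol 3.1.2, repeated in SAP 3.2.2, lists four secondary endpoints on the time scale:

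- "Time to first confirmed worsening on the adjusted INCAT disability scale by at least 1 point from the value at Baseline"
- "Time to first confirmed worsening on the I-RODS scale"
- "Time to 1 point decrease (improvement of disability) in adjusted INCAT disability score"
- time to a decrease in I-RODS.

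For their analysis, Protocol 9.2.2 states that "All efficacy endpoints detailed in Sections 3.1.2 and 3.1.3 will be summarized by means of descriptive statistics". It adds that tables and graphs should let the dose groups be compared where feasible.

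The SAP is more specific. Its Document History records, as an addition in version 3, "Kaplan-Meier analysis for time-to response variables". SAP 10.1 says of INCAT: "The time to first response and time to first worsening will be examined and presented by means of a Kaplan-Meier analysis". SAP 10.2 extends this to I-RODS, grip strength and MRC. SAP 8 says of time-to-event summaries: "These parameters might not be tabulated separately, but can be included as an inset into a Kaplan-Meier plot". The introduction to SAP 10 says: "This study will furthermore compare all efficacy endpoints between the different dosing groups".

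The other endpoint types get an explicit dose contrast. For responses, SAP 10.1 and 10.2 plan logistic regression with odds ratios and 95% CIs, and Protocol 9.2.2 adds confidence intervals for differences in response rates. For continuous scores, SAP 10.2 plans ANCOVA with differences in least square means between factor levels.

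**The concern.** The only confirmatory test compares the 1.0 g/kg arm with a fixed threshold, so what the trial says about dose comes entirely from secondary comparisons. Protocol 3.3.2 expects that the lower dose may be too little for some patients and treats it as a partial stand-in for placebo. Time to worsening addresses that expectation most directly. As planned, a reader gets a Kaplan-Meier curve for each dose, perhaps with event rates in an inset, and must judge by eye whether curves or separate intervals differ. That is less sensitive than an interval for the difference, and it takes no account of randomization stratum, CIDP variant or baseline score, which the SAP already adjusts for elsewhere.

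**Working it through.** **1. What is planned for each endpoint type**

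| Endpoint type | Between-dose estimate with interval | Where |
|---|---|---|
| Response (INCAT, I-RODS, grip, MRC) | Odds ratio, 95% CI; CI for difference in rates | SAP 10.1, 10.2; Protocol 9.2.2 |
| Continuous scores | Difference in least square means from ANCOVA | SAP 10.2 |
| Time to event | None named | SAP 10.1, 10.2 |

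Neither document names a log-rank test, a Cox model, a hazard ratio, a difference in Kaplan-Meier probabilities or medians, or a restricted mean. The SAP does not say outright that Kaplan-Meier is done by dose group. That follows from the general rules in SAP 8 and 10.2.

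**2. The plan's own figure**

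The documents give no event rate, hazard ratio or power for a time-to-event endpoint. The one sample-size figure is 62 evaluable patients at 1.0 g/kg (Protocol 9.1). With the lower Wilson limit

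(p + z²/2n − z√(p(1−p)/n + z²/4n²)) / (1 + z²/n),

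n = 62 needs at least 34 responders (lower limit 0.4253). Exact power at 60% is 83.1%. At n = 61 it is 79.2%, and from 62 up to 72 (as far as checked) it stays above 80%. So 62 reproduces, but it sizes only the primary endpoint. Enrolment of 140 at 1:2:1 gives 35, 70 and 35.

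**3. How precise a hazard ratio would be**

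For one contrast, 70 v 35, Var(log HR) ≈ 1/(d × 2/3 × 1/3) = 4.5/d, where d is the number of events. The 95% CI is the estimate divided and multiplied by exp(1.96 × √(4.5/d)). The event shares are assumptions.

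| Share with event | d | CI factor | Power, HR 1.5 | Power, HR 2 |
|---|---|---|---|---|
| 20% | 21 | 2.48 | 14% | 32% |
| 40% | 42 | 1.90 | 24% | 56% |
| 60% | 63 | 1.69 | 33% | 74% |
| 80% | 84 | 1.57 | 42% | 85% |

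Power of 80% would need 74 events at HR 2 and 215 at HR 1.5. The estimate is feasible but imprecise.

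**4. Gain over comparing separate intervals**

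Assumed: 70 v 35 patients; visits every 3 weeks; 30% worsening by Week 24 at 1.0 g/kg; no dose effect before Week 3, because all arms have had only the common loading dose; 35% leaving their randomized dose at Week 6, at random. The dose effect then acts for 21 of 24 weeks. Before any exits, worsening at 0.5 g/kg would be 1 − 0.7^(1/8 + 7/8 × 2) = 1 − 0.7^1.875 ≈ 49% for HR 2, and 1 − 0.7^2.3125 ≈ 56% for HR 2.5.

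| HR after Week 3 | Contrast 95% CI excludes no effect | Per-arm 95% CIs at Week 24 do not overlap |
|---|---|---|
| 2 | about 35% | about 12% |
| 2.5 | about 52% | about 24% |

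At HR 2 the Cox estimate falls to about 1.8, because the first three weeks dilute it. A simpler simulation with a constant hazard ratio from Week 0, 11% random loss (8/70) and no exit at Week 6 gives 56% v 25% and 81% v 52%. Those figures ignore two features of this design and are too favourable.

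**The case against.** The strongest reply is that the dose comparisons are deliberately descriptive. Protocol 9.2.2 and SAP 10.1 speak of comparing doses by side-by-side presentation, and SAP 10.2 promises tables and graphs that allow direct comparison. Kaplan-Meier by dose group meets that. A reader might infer that the plan contradicts its own statement that all efficacy endpoints will be compared. It does not: the comparison is unspecified, not denied. This part of the reply stands.

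A reader might also infer that no dose effect on improvement or worsening is estimated at all. That is too strong. Week 24 response gets odds ratios with intervals. SAP 8 allows event rates, and confidence intervals as appropriate. SAP 10.2 tabulates deteriorations by dose group and by their effect on disposition. What is missing is an estimate on the time scale, and any model-based contrast for worsening.

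The SAP's list of exploratory models is open-ended and its output list is deferred to a separate document. This softens the point only a little, since an analysis that is not named is not pre-specified.

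Finally, a hazard ratio has real problems here. The first randomized dose comes at Week 3, so proportional hazards cannot be expected to hold exactly. Patients stable at Week 6 or deteriorating go to rescue in the 0.5 and 1.0 g/kg arms and drop out in the 2.0 g/kg arm. SAP 8.4 censors time to response at the start of rescue and gives no censoring rule for time to worsening. Censoring therefore depends on outcome and differs in form between arms. This stands, but it affects the planned Kaplan-Meier curves as well. It is a reason to state rules and caveats, not to leave the estimate out.

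**Conclusion.** The gap is real and modest. No between-dose estimate with an interval is planned for any of the four time-to-event endpoints, and worsening has no model-based dose contrast. No document statement is broken and the primary analysis is untouched, so this is a cheap improvement and not an error.

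Under the assumed values, an interval for the contrast would show an effect roughly two to three times as often as non-overlap of per-arm intervals (35% v 12% at HR 2; 52% v 24% at HR 2.5). This rests on an assumed 30% worsening rate, assumed hazard ratios, and a 35% exit at Week 6 treated as random, although in the trial exit depends on outcome. Non-overlap is also only a stand-in for how readers look at curves; neither document proposes it as a rule. The direction of the gain is firmer than its size. Because the estimates would be imprecise, they suit exploratory estimation and not a formal test.

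**What to change.** In SAP 10.1 and 10.2, for each time-to-event endpoint:

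1. Add an exploratory estimate with 95% CI for 0.5 v 1.0 g/kg and 2.0 v 1.0 g/kg. This can be a difference in Kaplan-Meier probability at Week 24, a Cox hazard ratio, or both. For Cox, use Efron or discrete handling of ties, since events are seen only at 3-weekly visits, and the terms already in the logistic model: dose group, randomization stratum, CIDP variant and baseline score.
2. State that proportional hazards is not expected to hold exactly, because all arms share the loading dose until Week 3. The difference in probability does not need that assumption.
3. State the censoring rule for time to worsening. Note that censoring at rescue or drop-out depends on outcome and takes a different form in the 2.0 g/kg arm.
4. Settle the direction of the I-RODS decrease endpoint before modelling. SAP 8.4 treats a negative MCID-SE as deterioration, yet worsening on I-RODS is already listed separately.

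The cost is SAP wording and one or two extra procedure calls per endpoint. No new data, change in conduct or alpha is needed. The downside is a few more imprecise exploratory estimates that carry the proportional-hazards and informative-censoring caveats.
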